2.0 OBJECTIVES AND SCIENTIFIC AIMS

Primary objective

To evaluate the ability of colesevelam to improve lenalidomide-associated diarrhea in patients with multiple myeloma treated with lenalidomide maintenance. Diarrhea will be evaluated using Common Terminology Criteria for Adverse Events (CTCAE) grading. The primary end-point is improvement of diarrhea by at least 1 grade or returns to patients baseline when receiving colesevelam according to CTCAE 5.0 scale by 4 weeks of treatment with colesevelam.

Secondary objective

- To assess GI symptoms using the Patient Reported Outcomes within the Common Terminology Criteria for Adverse Events (PRO-CTCAE)
- To assess diet before and while on treatment with colesevelam.
- To further describe diarrhea during the study period using the Bristol Stool Form Scale.3
- Describe duration of response by week 12 (end of study)

Correlative studies

- To assess lenalidomide pharmacokinetics while on colesevelam
- Collection of research stool samples for GI microbiota and bile acid assessment

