4.0 OVERVIEW OF STUDY DESIGN/INTERVENTION

4.1 Design

This is a single institution, single arm, open label phase II trial to evaluate the efficacy of colesevelam for myeloma patients on lenalidomide maintenance who experience grade 1 or more diarrhea. Patients will be given colesevelam at a starting dose of 2 tablets (2 x 625 mg) which can be increased to up to 6 tablets per day depending on efficacy and tolerability, see dose adjustment schedule section 9.2, page 16. Patients can continue on the study until unacceptable toxicity, diarrhea that remains grade 1 or higher at week 4, worsening of diarrhea at any point, or end of study (12 weeks), whichever comes first. Each patient will be followed for a total 12 weeks.

The primary endpoint of this study is improvement of diarrhea. Response is defined as improvement by at least 1 grade according to CTCAE version 5.0 (see page 15) or returns to patients baseline when receiving colesevelam. A total of 25 patients will accrue on the study in a Simon's two-stage minimax design. In the first stage of the study, 16 patients will accrue. If 1 or fewer patients have a reduction in diarrhea severity, the study will stop due to a lack of efficacy; otherwise, an additional 9 patients will accrue. We estimate that the accrual to the study will be approximately two patients per month. The study is expected to be completed in approximately two years.

A diarrhea diary will be filled out by patients to capture frequency and consistency of bowel movements. GI symptoms will be assessed using the GI oriented PRO-CTCAE questions. Diet will be recorded at several time points to assess changes in dietary intake prior to and while on colesevelam. Stool consistency will be assessed using the Bristol Stool Form Scale. Correlative studies include pharmacokinetic (PK) evaluation of lenalidomide as well as collection of stool for studies of the GI microbiome.

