6.0 CRITERIA FOR SUBJECT ELIGIBILITY

6.1 Subject Inclusion Criteria

Patients must meet all the following criteria to be eligible for treatment on study:

- Memorial Sloan Kettering Cancer Center (MSK) confirmed diagnosis of multiple myeloma
- Treatment with single agent lenalidomide maintenance
- Patient must be ≥18 years of age at the time of informed consent
- Experiencing grade 1 or more diarrhea according to the CTCAE 5.0 criteria for at least 4 out of 7 days preceding screening and study inclusion.
- Scheduled to receive lenalidomide maintenance cycles at MSK
- Willingness and ability to comply with scheduled visits, treatment plan, laboratory tests and other study procedures

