10.5 Symptom and diet assessments (secondary endpoints)

GI symptoms will be assessed at each follow-up (baseline; day 1 of colesevelam), at 1 week (+/- 2 days), 2 weeks (+/- 2 days), 4 weeks (+/- 7 days), and at 12 weeks (+/- 7 days) and will be instructed to fill in the GI oriented PRO-CTCAE questionnaire. The PRO-CTCAE for Gastrointestinal Symptoms is a 10-item multiple choice questionnaire using a 5-point Likert-type response format (Appendix 4). There is no composite score for this instrument. All items in this questionnaire will be analyzed individually.

Diet will be recorded using a questionnaire for dietary intake at set time points during the study (Appendix 5). In the diet questionnaire, patients will record their dietary intake at baseline and at the follow up at week 1, 2, 4, and 12 after starting colesevelam. We will record dietary intake and ask whether the patients have changed their diet as a results of the diarrhea and/or lenalidomide or colsevelam treatment.

Consistency of bowel movements will be graded using the Bristol Stool Form Scale which was developed for patient use.³ Bristol Stool Form Scale categorizes stools into one of seven types based on stool consistency (Appendix 3).

These questionnaires together take between 10 and 20 minutes to complete. These instruments will be given to the patient at the start of the study and will be handed in at clinical visits or can be sent to MSK in the event that visits are replaced by a phone call (see section 4.2).

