10.10 Table 4. Overview of time points for sampling and clinical assessment

	Baseline	Cycle 1 Day 1 (Within 14 days of baseline)	Cycle 1 Day 8 (+/-7 days)	Cycle 1 Day 15 (+/-7 days)	4 weeks/ End of Cycle 1 (+/- 14 days)	12 weeks / End of Cycle 3 (+/- 21 days)
MD/RN assessment	Visit		Visit or telephone assessment	Visit or telephone assessment	Visit or telephone assessment	Visit
Stool studies GI pathogens ^a	Xa					
Triglycerides	X					
CBC	X					X
Comp	X					X
SPEP, IFE and FLC	X					X
Stool Diary (response assessment) and Bristol Stool Scale ^b	Х		X	х	Х	Х
PRO-CTCAE	X		X	Х	Х	Х
Nutritional Survey ^c						Х
PK studies ^d		Χq	Xq			
Research stool samples ^e	Х					X

- a. Stool studies for GI pathogens should be collected prior to starting colesevelam but do not need to be resulted prior to starting Day 1 dose of colesevelam, unless infection is suspsected by the treating investigator.
- b. Response assessments (Stool diaries) will be done at Cycle 1 Day 8, Cycle 1 Day 15, end of Cycle 1 (week 4) and end of Cycle 3 (week 12). If diarrhea does not improve by at least 1 grade from baseline (using CTCAE version 5.0) or to patient's baseline bowel pattern by the end of Cycle 1 they will be removed from study.
- c. Patients will complete one nutrtional survey ("Food and Activitity Questionaire" survey will be used) and return at week 12 visit.

- d. Lenalidomide pharmacokinetics will be assessed in up to 15 patients to assess possible drug interactions between lenalidomide and colesevelam. In these patients, a blood sample will be drawn pre- and 2 hours post the first colesevelam dose (day 1), as well as pre- and 2 hours post colesevelam on day 8 after initiation of colesevelam.
- e. Research stool samples will be collected at baseline and after 12 weeks of treatment for microbiota and bile acid studies.

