12.0 CRITERIA FOR THERAPEUTIC RESPONSE/OUTCOME ASSESSMENT

Response is defined as improvement in diarrhea by 1 grade according to the CTCAE 5.0 scale or returns to patients baseline. Resolution of diarrhea is defined as normalization of bowel habits (grade 0). Response grading according to CTCAE 5.0 definition will be assessed at baseline and after 1 week, 2 weeks, 4 weeks and the end of study at 12 weeks. When evaluating the primary endpoint based on CTCAE 5.0, the grading will be determined by recalling the average number of stools in the previous two days. In addition, GI symptoms and diet will be assessed and at baseline and after 1 week, 2 weeks, 4 weeks and at the end of study at 12 weeks.

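### Table 4 schedules one nutritional survey, returned at week 12, while the text schedules diet records at baseline and weeks 1, 2, 4 and 12; under Table 4 no pre-colesevelam diet record is scheduled

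*Combined protocol and SAP*

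**What the plan says.** Diet is a stated secondary objective. Section 2.0 lists "To assess diet before and while on treatment with colesevelam". Section 4.1 carries this into the design: "Diet will be recorded at several time points to assess changes in dietary intake prior to and while on colesevelam". Section 8.5, part of the pretreatment evaluation, provides for a dietary questionnaire.

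Two sections give the time points. In section 10.5, "patients will record their dietary intake at baseline and at the follow up at week 1, 2, 4, and 12 after starting colesevelam". In section 12.0, "GI symptoms and diet will be assessed and at baseline and after 1 week, 2 weeks, 4 weeks", followed by the end of study at week 12.

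Table 4 in section 10.10 differs. Its Nutritional Survey row is marked only in the 12-week column, and footnote c reads "Patients will complete one nutrtional survey", names a food and activity questionnaire, and fixes the week 12 visit for its return.

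For the analysis, section 14.0 reports the proportion of patients whose diet changed because of diarrhea and the proportion whose diet changed because of lenalidomide or colesevelam. It also aims to see whether patients resume their normal diet if the diarrhea responds.

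**The concern.** Study staff usually work from the schedule of assessments. Staff who follow Table 4 would collect no diet record before the first colesevelam dose, and such a record cannot be obtained prospectively afterwards. The comparison promised in sections 2.0 and 4.1 would then have no starting value, and the section 14.0 proportions would depend on what patients remember at week 12.

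A second question is who would supply the single survey. Several rules take patients without sufficient improvement off study well before week 12. If those patients return nothing, the diet results describe mainly patients who improved, and section 14.0 does not say how missing diet data enter the denominators.

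**Working it through.** The plan states no figure to reproduce here, so the check is a count of scheduled records and a comparison of the sections.

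**1. Records per patient under Table 4.** The Nutritional Survey row has one mark, at 12 weeks. Baseline, Day 1, Day 8, Day 15 and week 4 are empty. Total = 1; before colesevelam = 0. Footnote c says the same in words, so a broken table does not explain the result.

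**2. Records per patient under sections 10.5 and 12.0.** Baseline (1) plus weeks 1, 2, 4 and 12 (4) gives 1 + 4 = 5; before colesevelam = 1.

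**3. Difference.** 5 − 1 = 4 records per patient, of which 1 − 0 = 1 is the pre-colesevelam record.

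**4. Is the rest of Table 4 out of step too?** The PRO-CTCAE row is marked at baseline, Day 8, Day 15, week 4 and week 12, which is 5 time points and agrees with section 10.5. Of these two questionnaires, only diet departs from the text.

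**5. Can the two schedules be reconciled by reading them together?** Section 10.5 says of the questionnaires: "These instruments will be given to the patient at the start of the study". Footnote c fixes when the survey is returned, so a patient could fill it in early. But one completed form yields one record, and comparing diet before with diet during treatment needs at least two. If the form asks about both periods, the answer for one of them is recall; its content is not shown.

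**6. What each diet result needs.**
- Diet before against during colesevelam (sections 2.0 and 4.1): two dated records. Available under the text, not under Table 4.
- Diet change due to diarrhea or lenalidomide (section 14.0): self-report under either schedule. Both exposures precede entry, since eligibility requires "Treatment with single agent lenalidomide maintenance" and current diarrhea. Section 10.5 plans to "ask whether the patients have changed their diet as a results of the diarrhea and/or lenalidomide or colsevelam treatment".
- Diet change due to colesevelam (section 14.0): self-report, which a baseline record could support. Under Table 4 it is recall at week 12 alone.
- Return to normal diet after response (section 14.0): concerns responders, so a survey mainly from responders is less of a problem for this aim.

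**7. Who returns a week 12 survey.** Removal for insufficient improvement is set at 2 weeks in sections 9.2 and 9.3, at 2 weeks after reaching dose level 2 in section 13.0, and at the end of Cycle 1 in Table 4 footnote b. Sections 1.0 and 4.1 say each patient is followed for 12 weeks. No section says whether a removed patient still returns the survey, so selection toward patients who improved is possible but not established.

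**The case against.** The strongest reply is that Table 4 may be what is intended. Footnote c is specific: it gives the number of surveys, the instrument and the return visit. Section 14.0 contains no paired diet analysis, only proportions obtained by asking patients, and a single survey can supply those if it asks the right questions. This has weight. It means the documents do not settle which schedule is intended, and that the specified analysis loses less than the objective does. It does not remove the conflict, because sections 2.0, 4.1, 8.5, 10.5 and 12.0 would then all describe data that are not collected.

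A reader might infer three stronger things that the documents do not support.
- *That no baseline diet information could exist.* The forms are handed out at the start, so one could be completed early. What can be said is that no baseline record is scheduled.
- *That only 10% to 30% of 25 patients would return the survey.* Those rates in section 14.0 are decision thresholds for response by week 4; they are not retention at week 12. Applying 10% to 25 patients also ignores the stage 1 stop after 16 patients, which has an exact probability of 0.515 at that rate. Nor is it stated that removed patients return nothing.
- *That the primary result is compromised.* The case series in section 3.0 reports two patients who improved on a low-fat diet alone, which makes diet worth recording. But the response definition and the two-stage rule use no diet data.

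The instrument references are a clerical matter. Sections 8.5 and 10.5 place the diet questionnaire in Appendix 5, and section 10.9 cites Appendix 5 for the medication diary, which sections 4.2 and 20.0 place in Appendix 1. The questionnaire named in footnote c may be the same form as the dietary questionnaire; the appendix contents are not in the text available.

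**Conclusion.** The inconsistency is real and lies in current text: 1 scheduled diet record per patient in Table 4 against 5 in sections 10.5 and 12.0, and 0 scheduled before colesevelam against 1. These counts rest on no assumption about response or retention.

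If Table 4 is followed, the objective in section 2.0 cannot be met by comparing records, and the section 14.0 diet proportions become recall at week 12. That they would also come mainly from patients who improved holds only if removed patients do not return the survey, which the documents leave open; its size cannot be estimated from them.

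Severity is minor. The effect is confined to a descriptive secondary objective, and the primary endpoint, sample size and decision rule stand.

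**What to change.** Align the Nutritional Survey row of Table 4 and footnote c with sections 10.5 and 12.0: baseline and weeks 1, 2, 4 and 12, with a baseline record as the minimum. Name one diet instrument for all time points. In section 14.0, report each diet proportion with the number of patients who have diet data. Correct the double use of Appendix 5 at the same time.

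The cost is an edit to one table row, one footnote, one clause in section 14.0 and the appendix references, plus up to 4 more questionnaires per patient. No visits are added, because those contacts already carry PRO-CTCAE. Section 10.5 puts its questionnaires together at 10 to 20 minutes, but the length of the footnote c survey is not shown, so the added burden should be checked.

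If a single week 12 survey is intended, amend sections 2.0, 4.1, 8.5, 10.5, 12.0 and 14.0 instead, and describe the result as week 12 self-report among patients who returned the survey. That adds no patient burden but gives up the before-and-during comparison. Either way, state whether patients removed early are asked to return the survey.

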11.0 TOXICITIES/SIDE EFFECTS

Colesevelam (Welchol®) is provided to investigator by Daiichi Sankyo, Inc.

In clinical trials, the most common side effects with colesevelam (incidence \geq 2% greater than placebo) include constipation, dyspepsia, and nausea. In trials including patients with diabetes, the overall incidence of hypoglycemia was 3.0% in colesevelam-treated patients and 2.3% in placebo-treated patients.

Postmarketing reports with concomitant colesevelam administration include drug interactions with phenytoin, warfarin, and thyroid hormone replacement therapy (section 3.0, page 9). These medications should be administered >4 hours prior or after colesevelam and the serum concentration and therapeutic effect should be monitored. Other postmarketing reports include bowel obstruction, dysphagia, esophageal obstruction, fecal impaction, hypertriglyceridemia, pancreatitis, and increased transaminases.

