4.2 Intervention

All patients should be on maintenance single agent lenalidomide and experiencing grade 1 or higher diarrhea according to the CTCAE grading system. For treatment with colesevelam, the starting dose will be 1250 mg (2 x 625 mg) with food which can be increased to 6 tablets max per day based on efficacy and tolerability. Coleveselam should not be taken within 4 hours before or after lenalidomide and other interacting medications. All participants will be given a pill diary to record intake of colesevelam (Appendix 1). The effect of colesevelam on lenalidomide-associated diarrhea will be evaluated after 1, 2, 4, 12 weeks after start of treatment. If the diarrhea does not respond to the starting dose of colesevelam, the dose can be increased every 2 days to 2 tablets two times per day (2 x 625 mg BID) and later to 3 tablets two times per day (3 x 625 mg BID). The colesevelam dose can be decrease to 1 tablet per day if there has been improvement of diarrhea but emergence of side effects. Treatment with colesevelam will continue until drug-related toxicity, diarrhea that remains grade 1 or higher at week 2 despite dose elevations, or if worsening diarrhea occurs, or up to 12 weeks on study.

Patients will be evaluated by their physician and/or research nurse at baseline, after 1 week (+/- 2 days), after 2 weeks (+/- 2 days), after 4 weeks (+/- 7 days), and 12 weeks (+/- 7 days) for efficacy, toxicity, and compliance. The evaluations after 1, 2, and 4 weeks will preferably as office visits but can be replaced by telephone calls for sake of convenience.

Pharmacokinetics will be assessed in a subset of patients (up to 15 patients) at baseline and 8 days after start of colesevelam. All patients will be asked to participate in the PK studies and the first 15 who consent to this correlative part will be included. Research stool samples will be collected for all study participants at baseline and after 12 weeks of study.

Patients that repond to colesevelam can continue on the drug after the 12 weeks of study treatment. Coverage for colesevelam costs after the 12 weeks will not be covered by the trial but will go through patient's insurance.

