6.2 Subject Exclusion Criteria

- Patients with history of bowel obstruction
- Patients with serum triglyceride levels >300 mg/dL
- Patient with history of hypertriglyceridemia-induced pancreatitis
- Patients with known hypersensitivity to colesevelam or any component to the formulation
- Patients currently already receiving a bile acid sequestrant or have previously used bile acid sequestrant drugs for diarrhea and had no benefit
- Patients with diarrhea secondary to infection. Stool studies for GI pathogens should be collected prior to starting colesevelam but do not need to be resulted prior to starting Day 1 dose of colesevelam, unless infection is suspsected by the treating investigator, in which case Clostridium difficile PCR when clinically indicated, GI pathogen panel, stool ova and parasites, Giardia and Cryptosporum stool antigen tests will need to be resulted at investigator discretion.

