8.2 Laboratory assessment

The following studies and laboratory tests will be completed within 0-14 days prior to colesevelam treatment:

- Complete blood count with differential count
- Comprehensive metabolic panel: sodium, potassium, chloride, carbon dioxide, serum creatinine, glucose, blood urea nitrogen (BUN), EGFR, albumin, calcium, magnesium, phosphorus, alkaline phosphatase, ALT, AST, total bilirubin, direct bilirubin, uric acid, LDH, total protein
- Serum protein electrophoresis (SPEP) and serum immunofixation to assess for presence and quantity of monoclonal protein (M-protein)
- Serum free light chain studies
- Quantitative immunoglobulins
- Serum triglycerides

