9.1 Treatment regimen

Only patients with grade 1 or more (CTCAE grading) diarrhea while on lenalidomide maintenance can initiate treatment with colesevelam on the study.

The treatment arm will be:

- The starting dose of colesevelam is 1250 mg (625 mg x 2) with food once daily and dose can be increased (6 tablets max per day) based on tolerability and efficacy
- Colesevelam should be spaced out from lenalidomide and other interacting medications by at least 4 hours

- Colesevelam is given continuously and patients will be treated for up to 12 weeks on study
- Treatment will continue until drug-related toxicity, worsening diarrhea, or unimproved diarrhea at 2 weeks despite increased dosage of the study drug or for a maximum of 12 weeks of treatment
- Patients who respond can continue on colesevelam after the 12 weeks of study treatment. Coverage for colesevelam costs after the 12 weeks will not be covered by the trial but will go through patient's insurance.

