9.2 Dose adjustments

Colesevelam dosing can be adjusted based on tolerability and efficacy using Table 3. The dose of colesevelam can be increase or decreased at the invesitgator's discretion based on tolerability at any timepoint as long as changes and reason are documented. If Revlimid is held, colesevelam can be held at the same time.

Table 3. Dose levels and escalation/de-escalation for colesevelam

Dose level	Dosing of Colesevelam	Dose adjustment		
0	1250 mg (2 tablets) daily	Starting dose		
1	1250 mg (2 tablets)	Increase if diarrhea remains grade 1 or		
	twice daily	higher after 2 days on each dose level		
2	1875 mg (3 tablets)	Increase if diarrhea remains grade 1 or		
	twice daily	higher after 2 days on each dose level		
-1	625 mg daily	Decrease if improvement of diarrhea		
		but emergence of side effects		

Indications for discontinuation of study medication:

- If patients cannot tolerate dose level -1 then patients should discontinue treatment and come off study
- If patient has worsening of diarrhea within the first week after starting colesevelam, they should discontinue treatment and come off study
- If the diarrhea remains grade 1 or higher after 2 weeks of treatment

The investigator may *consider* withdrawing patients from the study for any of the following reasons:

- Side effects from colesevelam
- If there is protocol violation
- Non-compliance
- Administrative reasons
- Failure to return for follow-up

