10.2 Laboratory assessment

Laboratory assessment will include:

- Complete blood count with differential count
- Comprehensive metabolic panel: sodium, potassium, chloride, carbon dioxide, serum creatinine, glucose, blood urea nitrogen (BUN), EGFR, albumin, calcium, magnesium, phosphorus, alkaline phosphatase, ALT, AST, total bilirubin, direct bilirubin, uric acid, LDH, total protein
- Serum protein electrophoresis (SPEP) and serum immunofixation to assess for presence and quantity of monoclonal protein (M-protein)
- Serum free light chain studies
- Quantitative immunoglobulins

Hematology and chemistry panels will be performed during screening, at 4 weeks (+/-7 days), and at the end of trial (12 weeks +/-7 days).

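### Triglycerides are checked at entry and hypertriglyceridemia is a named risk, but no triglyceride test is scheduled on treatment; the week 12 draw could carry one

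*Combined protocol and SAP*

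**What the plan says.** Two exclusions in Section 6.2 concern triglycerides: "Patients with serum triglyceride levels >300 mg/dL", and a history of pancreatitis caused by hypertriglyceridemia. Section 8.2 puts serum triglycerides on the pretreatment list, introduced by "The following studies and laboratory tests will be completed within 0-14 days prior to colesevelam treatment". Section 8.0 allows the sample to be taken at baseline and the drug to be started, with the patient taken off study later if ineligible.

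Section 11.0 lists the risks seen after marketing: "Other postmarketing reports include bowel obstruction, dysphagia, esophageal obstruction, fecal impaction, hypertriglyceridemia, pancreatitis, and increased transaminases". It gives no frequency for any of them.

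On treatment, Section 10.2 lists blood count, metabolic panel, protein electrophoresis with immunofixation, free light chains and immunoglobulins. Triglycerides are not listed. On timing it says "Hematology and chemistry panels will be performed during screening, at 4 weeks (+/-7 days), and at the end of trial (12 weeks +/-7 days". Table 4 ("Overview of time points for sampling and clinical assessment") has one triglyceride mark, under Baseline. It marks the blood count, chemistry and myeloma tests at baseline and week 12, and no laboratory test at week 4.

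After the study period, Section 9.1 says "Patients who respond can continue on colesevelam after the 12 weeks of study treatment".

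**The concern.** The plan treats triglycerides as important enough to decide entry and names their rise as a reported effect of the study drug, then schedules no further measurement. Most of the other reports named in Section 11.0, such as obstruction, dysphagia, impaction and pancreatitis, would ordinarily show themselves through symptoms. Raised triglycerides may not, so finding them depends on a blood test.

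What is at stake is the safety of individual patients. Colesevelam may be given at up to 6 tablets a day for up to 12 weeks, and responders may then stay on it outside the trial. The week 12 draw is the last planned study blood sample before that longer use.

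**Working it through.** **Step 1: compare the schedule entries.**

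| Place | Before treatment | On treatment |
|---|---|---|
| 6.2 | above 300 mg/dL excluded | no limit given |
| 8.2 | triglycerides listed | not applicable |
| 10.2 | see 8.2 | triglycerides absent; ALT and AST listed |
| Table 4 | one triglyceride mark (Baseline) | no triglyceride mark; chemistry marked at week 12 |

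Section 10.2 and Table 4 agree, so the omission is not an artefact of a broken table. Scheduled triglyceride values per patient: 1 before treatment, 0 on treatment.

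**Step 2: compare the named laboratory risks.** Two reports in Section 11.0 are themselves laboratory findings: increased transaminases and hypertriglyceridemia. The first is covered on treatment by ALT and AST in Section 10.2. The second is not covered.

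**Step 3: check whether a general safeguard supplies the test.** Section 10.8 grades laboratory abnormalities that are found. Section 13.0 requires withdrawal for unacceptable toxicity. Section 17.0 promises careful laboratory monitoring but names no triglyceride test. None of them schedules one.

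**Step 4: exposure.** Maximum dose (Section 9.2, dose level 2): 6 × 625 mg = 3,750 mg per day, on study for up to 12 weeks.

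**Step 5: size of the fix.** Evaluable sample: 16 + 9 = 25 (Section 14.0). Patients replaced under Section 14.0 leave before the week 1 evaluation, so they add no week 4 or week 12 assays.

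- Week 12: at most 25 × 1 = 25 assays.
- Week 4, if that draw takes place: at most another 25, so at most 25 + 25 = 50 in all.

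The documents do not say how many patients will reach week 12. As a rough illustration, assume that only responders remain: 25 × 0.30 = 7.5 (about 8) at the target rate and 25 × 0.10 = 2.5 (about 3) at the unpromising rate. These figures are approximate, because responding and remaining on treatment are not the same. A patient who improves from grade 3 to grade 1 has responded under Section 12.0, yet meets the discontinuation rule in Section 9.2.

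**Step 6: effect on the design.** The plan's Simon two-stage design stops if 1 or fewer of 16 respond and is promising if more than 4 of 25 respond. Its exact success probability is the sum over x = 2 to 16 of P(X1 = x) × P(X2 ≥ 5 − x), with X1 ~ Bin(16, p) and X2 ~ Bin(9, p).

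- p = 0.10: type I error 0.0951.
- p = 0.30: power 0.9030, so type II error 1 − 0.9030 = 0.0970.

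Both errors are within the stated 0.10. A triglyceride assay enters none of these terms, so they do not change.

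**The case against.** The strongest reply is that this is a choice about monitoring intensity. The drug is marketed, the study is IND exempt, and study exposure is at most 12 weeks. Patients most at risk are screened out. Hypertriglyceridemia appears only in a list of postmarketing reports, not among the potential adverse events in Table 1. Investigators may order a test, may lower the dose for tolerability, and must withdraw patients for unacceptable toxicity. All of this stands and keeps the point minor. It does not supply the missing measurement, because an asymptomatic rise gives no prompt to order one.

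It is also fair to say that a test at the end of study dosing does not protect a patient during those 12 weeks. The week 12 value mainly informs the decision to continue the drug; a week 4 value would help earlier.

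A reader might infer four stronger things that the documents do not support:

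- *That a measured rise would go unreported because Section 17.2 counts only some abnormal values as adverse events.* Section 16.0 already summarizes laboratory data descriptively and against institutional normal ranges, so a measured value would appear there.
- *That one week 12 assay closes the gap.* Section 9.2 ends treatment "If the diarrhea remains grade 1 or higher after 2 weeks of treatment", and other sections also remove patients before week 12.
- *That unmonitored time at the top dose can be given as one number of days.* Section 9.2 sets removal at 2 weeks of treatment, Section 4.1 and Table 4 footnote b at week 4, and Section 13.0 at 2 weeks after dose level 2 is reached.
- *That the day 8 pharmacokinetic sample could serve instead.* It covers up to 15 patients and is timed to a colesevelam dose taken with food, so the post-dose sample would normally follow a meal.

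**Conclusion.** The point holds as a minor safety-monitoring gap. The plan screens on triglycerides and names their rise as a reported effect, but schedules no value after treatment starts. Its size is 0 scheduled on-treatment values per patient, against 1 at week 12 with the fix for each patient who gets that far.

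The documents give no rate for triglyceride rises on colesevelam and no on-treatment action level. The number of cases the test would find therefore cannot be stated, and nothing here shows that patients would be harmed. The trial is also too small to estimate such a rate well; the value of the test lies with the individual patient. The cost ceiling assumes 25 evaluable patients who all reach the draw. The conclusion that the gap exists needs no numerical assumption, since Sections 8.2 and 10.2 and Table 4 show it directly. The primary endpoint, sample size and error rates are unaffected.

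**What to change.** - Add serum triglycerides to the list in Section 10.2 and mark them in Table 4 at the week 12 chemistry draw, which both places already plan.
- Add them at week 4 if the draw listed in Section 10.2 takes place. The sponsor should settle this first, because Table 4 shows no week 4 laboratory tests.
- Collect the sample under the same fasting conditions as the baseline sample where possible, so that the change from baseline can be read.
- Summarize the values with the other laboratory data under Section 16.0. The 300 mg/dL figure is an entry limit, not an on-treatment stopping rule; the response to a raised value is for the sponsor to decide.

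The cost is one line in Section 10.2, one mark in Table 4 (two with week 4), and the assays counted above, run on blood already drawn. No new visit or draw is needed. Patients removed before week 4 or week 12 may still be missed.
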